Appendix 1 Schedule of Assessments

Assessment	Screening (Day –28 to Day –1)	Baseline (Day 1) ^a	Month 1 (±3 days)	Month 3 (±3 days)	Month 6 (±3 days)	Month 9 (±3 days)	Month 12 (±3 days) ^b	Safety Follow-Up (±3 days) [°]	Early Discontinuation ^d
Informed consent/assent	xe								
Medical history ^f	х								
Eligibility criteria ^g	х								
Demographic data ^h	х								
Limited physical examination ⁱ	х	х		х	x	x	х		х
Concomitant medications ^j	х	х		х	x	x	х		х
Height and weight	х	х		х	x	х	х		х
Serum sample for serum drug concentration and immunogenicity assessments ^k		x	x	x	x	x	x		x '
Optional tests m	x				x		x		
NuSpin instruction/ training ⁿ		х							
Nutropin AQ v1.1 administration ^o		x	x	x	x	x	x		
Nutropin AQ v1.1 dose compliance p			x	x	x	x	x		x
Adverse events q	x	х	x	х	х	х	х	х	х

^a All baseline assessments should be performed before the first dose of study drug.

^b The Month 12 visit will serve as the study completion visit.

Nutropin AQ (Somatropin [rDNA origin])—Genentech, Inc. 58/Protocol ML29543, Version 2

Appendix 1 (cont.) Schedule of Assessments

- ^c The patient will be contacted by phone 28 ± 3 days after the Month 12 visit to collect adverse events.
- ^d Patients who discontinue from the study early will be asked to return to the clinic within 28 days after the last dose of study drug.
- ^e Written informed consent/assent must be obtained and documented before any study-specific screening procedure is performed.
- ^f Includes clinically significant diseases, surgeries, prior height and weight measurements, and all prescription medications used by the patient in the 30 days prior to the screening visit.
- ^g Historical laboratory tests include two GH stimulation tests with GH response < 10 ng/mL (obtained up to 12 months prior to informed consent/assent; see Section 4.1.1 for acceptable tests); thyroid function testing (obtained within 12 months prior to informed consent/assent); complete blood counts (obtained within 12 months prior to informed consent/assent); and for females, karyotype or SHOX analysis to exclude the diagnosis of Turner syndrome (obtained any time prior to informed consent/assent). Historical radiographic test includes bone age obtained within 12 months prior to enrollment. If results are not available within a specified timeframe, the tests that may be done as part of the screening process are CBC and X-ray for bone age. All other tests should be done as part of standard care.
- ^h Demographic data will include date of birth, sex, and self-reported race/ethnicity.
- ⁱ Limited physical examinations should be performed as per the standard of care guidelines for a child with GHD undergoing GH therapy. Pubertal status and confirmation of prepubertal status, presence of hip or knee pain, appearance of spine (i.e., appearance of significant scoliosis), and routine fundoscopic examination for absence of signs of intracranial pressure must be recorded. New or worsened clinically significant abnormalities after baseline should be recorded as adverse events, if applicable.
- ^j Concomitant therapy includes any medication (e.g., prescription drugs, over-the-counter drugs, herbal or homeopathic remedies, nutritional supplements, medications to manage multiple pituitary-hormone deficits as well as other chronic medications) used by a patient from 7 days prior to *dosing* to the study completion/early discontinuation visit.
- ^k A single blood sample will be collected at each visit during the treatment period *for immunogenicity and drug concentrations*. Process each sample for serum and split into four separate tubes for serum drug concentration and immunogenicity assessments (anti-GH antibody screening assay, anti-GH neutralizing antibody assay, and anti-GH antibody binding capacity assay). After baseline, blood samples *for immunogenicity and serum drug concentration* should be taken at least 12 hours after the last dose of Nutropin AQ v1.1 and prior to the next dose.
- ¹ The last blood sample at Month 12 must be drawn at least 12 hours after the last dose of Nutropin AQ v1.1. In the event of early discontinuation, an early discontinuation visit should be scheduled within 28 days after the last dose of Nutropin AQ v1.1 and a blood sample will be collected for a final assessment of serum drug concentration and immunogenicity.
- ^m Optional tests include a serum sample to test CBC at screening (if results are not available within 12 months prior to informed consent) and serum samples for IGF-1, which can be drawn at the discretion of the investigator at Month 6 and 12. All optional samples will be analyzed at the local laboratory. Optional tests also include an X-ray to determine bone age eligibility at screening only if the results are not available within 12 months prior to the enrollment date.
- ⁿ Nutropin AQ v1.1 will be administered via daily SC injections by the patient or caregiver. Instruction and training on Nutropin AQ v1.1 administration with the NuSpin device will be provided by a trained study nurse coordinator.

Nutropin AQ (Somatropin [rDNA origin])—Genentech, Inc.

59/Protocol ML29543, Version 2

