Historical laboratory and radiographic tests will be reviewed prior to obtaining informed consent and initiation of study drug. Study assessments will be scheduled at 3-month intervals following the baseline visit with an additional visit for the Month 1 blood draw, *which can be conducted at home with the help of a home health nurse*. Study assessments will include physical examinations, height and weight measurements, assessment of pubertal status, and collection of serum samples for study-specific laboratory assessments (serum drug concentration and immunogenicity assessments). Patients will otherwise be treated and followed as determined by their health care provider.

Nutropin AQ (Somatropin [rDNA origin])—Genentech, Inc.

17/Protocol ML29543, Version 2

Clinical Study Report: Nutropin AQ (Somatropin)—Genentech, Inc. 366/CSR ML29543

Patients who complete the Month 12 visit will be considered to have completed the study. Patients will be contacted by phone 28 (± 3) days after the Month 12 visit to collect adverse events.

Patients who discontinue from the study early will be asked to return to the clinic within 28 (± 3 days) days after the last dose of study drug for an early discontinuation visit, which will include the collection of serum samples for serum drug concentration and immunogenicity assessments.

Growth response will be monitored throughout the study. The annualized 6- and 12-month growth velocities for prepubertal patients will be analyzed. Growth velocities of patients who enter puberty during the study will not be included in the 6- and 12-month velocity analyses. However, these patients will remain in the study and their antibody data will be assessed. Safety assessments will consist of monitoring and recording of all serious and non-serious adverse events as outlined in Section 5.2.

Please see Appendix 1 for the schedule of assessments performed during the study.

Number of Patients

Approximately 80 patients will be enrolled at approximately 30 sites in the study in the U.S.

Target Population

Inclusion Criteria

Patients must meet the following criteria for study entry:

- Signed Informed Consent/Assent Form
 - The parent(s)/guardian(s) must be willing to give written informed consent; and
 - The child may be required to give written informed assent (if able, and dependent on state/Institutional Review Board requirements).
- Willing to adhere to the visit schedules and meet study requirements

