3.1 DESCRIPTION OF STUDY

This is a Phase IV, multicenter, open-label, single-arm study of somatropin (rDNA origin) (Nutropin AQ v1.1) in naïve prepubertal children with GHD. Approximately 80 patients will be enrolled at approximately 30 sites in the U.S. and will be treated with daily SC injections of Nutropin AQ v1.1 at a dose of *up to* 0.043 mg/kg/day (0.3 mg/kg/week, *which is the* approved and indicated dosage *for pediatric GHD*; refer to the USPI for Nutropin AQ) for 12 months. Dose adjustments may be made at the Month 6 visit *for changes in weight and insulin growth factor-1* (*IGF-1*) *levels, if measured*.

Screening will be performed within 28 days prior to Day 1 unless otherwise specified, after which eligible patients will initiate study treatment. *Patients who do not meet eligibility criteria may be re-screened once for this study. If during screening a subject is found to have an abnormal CBC, this test may be repeated within the same screening period at the discretion of the investigator and the subject may be enrolled if the second result is found to be normal per investigator assessment.*

Historical laboratory and radiographic tests will be reviewed prior to obtaining informed consent and initiation of study drug. Study assessments will be scheduled at 3-month intervals following the baseline visit with an additional visit for the Month 1 blood draw, *which can be conducted at home with the help of a home health nurse*. Study assessments will include physical examinations, height and weight measurements, assessment of pubertal status, and collection of serum samples for study-specific laboratory assessments (serum drug concentration and immunogenicity assessments). Patients will otherwise be treated and followed as determined by their health care provider.

Patients who complete the Month 12 visit will be considered to have completed the study. Patients will be contacted by phone 28 ± 3 days after the Month 12 visit to collect adverse events.

Patients who discontinue from the study early will be asked to return to the clinic within 28 days ($\pm 3 \ days$) after the last dose of study drug for an early discontinuation visit, which will include the collection of serum samples for serum drug concentration and immunogenicity assessments.

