4.5.3 Physical Examinations

Limited physical examinations should be performed as per the standard of care guidelines for a child with GHD undergoing GH therapy. Pubertal status and confirmation of prepubertal status, presence of hip or knee pain, appearance of spine (i.e., appearance of significant scoliosis), and routine fundoscopic examination for absence of signs of intracranial pressure must be recorded. New or worsened clinically significant abnormalities after baseline should be recorded as adverse events, if applicable.

Nutropin AQ (Somatropin [rDNA origin])—Genentech, Inc. 32/Protocol ML29543, Version 2

Clinical Study Report: Nutropin AQ (Somatropin)—Genentech, Inc. 381/CSR ML29543

4.5.4 Height and Weight

Height (three measurements at the same visit with a stadiometer or equivalently fixed measuring device) and weight will be recorded.

4.5.5 Laboratory Assessments

At screening, patients may be required to provide a blood sample to check for CBC, which will be analyzed at the local laboratory.

At Month 6 and 12 study visits, optional samples may be drawn to check IGF-1 levels, which will also be analyzed at the local laboratory.

For assessment of immunogenicity, samples will be drawn at each study visit (see Appendix 1) and will be sent to the central laboratory to assess the following:

- Serum drug concentration. GH concentration levels are necessary to interpret anti-GH antibody status and titers.
- Immunogenicity, utilizing the following assays:
 - anti-GH antibody screening assay
 - anti-GH neutralizing antibody assay
 - anti-GH antibody binding capacity assay

During the study treatment period, blood samples *for immunogenicity* should be drawn at least 12 hours after the last administration of Nutropin AQ v1.1 and prior to the next scheduled dose.

The last blood sample *for immunogenicity* at Month 12 must be drawn at least 12 hours after the last dose of Nutropin AQ v1.1. In the event of early discontinuation, an early discontinuation visit should be scheduled within 28 days after the last dose of Nutropin AQ v1.1 and a blood sample will be collected for a final assessment of serum drug concentration and immunogenicity.

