5.3.1 Adverse Event Reporting Period

Investigators will seek information on adverse events at each patient contact. All adverse events, whether reported by the patient or noted by study personnel, will be recorded in the patient's medical record and on the Adverse Event eCRF.

After informed consent has been obtained *but prior to initiation of study drug*, only serious adverse events caused by a protocol-mandated intervention should be reported (see Section 5.4.2 for instructions for reporting serious adverse events).

After initiation of study drug, all serious adverse events and non-serious adverse events, regardless of relationship to study drug, will be reported until 28 days after the last dose of study drug as provided in this study. After this period, the investigator should report any serious adverse events that are believed to be related to prior study drug treatment (see Section 5.6).

Nutropin AQ (Somatropin [rDNA origin])—Genentech, Inc. 37/Protocol ML29543, Version 2

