4.6.1 Exposure of Study Medication

Study medication is open label daily SC injections of Nutropin AQ v1.1 at a dose of up to 0.043 mg/kg/day (0.3 mg/kg/week) for 12 months. Dose adjustments may be made per investigator assessment at the Month 6 visit for changes in weight of at least \pm 2 kg from baseline or insulin growth factor-1 (IGF 1) levels, if measured.

The extent of exposure and compliance to study medication for each patient will be calculated as follows:

The extent of exposure to study medication (days) = (last study treatment date – date of initial dose) +1.

Compliance to study drug between visits = [1 - number of missed dose / (date of current visit – date of previous visit)] x 100%

The number and percentage of patients who complete study treatment or discontinue prematurely from study treatment will be summarized by reason for discontinuation of study medication. Descriptive statistics (mean, standard deviation, median, minimum, and maximum) of extent of exposure and compliance to study medication will be provided for all patients in the Safety Population.

Study medication administration data and compliance will also be presented in data listings.

4.6.2 Adverse Events

Verbatim descriptions of adverse events (AEs) will be mapped to Medical Dictionary for Regulatory Activities (MedDRA, version 20.1 or newer) preferred terms and System Organ Classes. The severity of AEs will be graded (1 - mild, 2 - moderate, 3 - severe, or 4 - life-threatening) according to Table 1 of the Protocol, and the relationship to study medication (yes vs. no) will be assessed by the investigator according to Table 2 of the Protocol.

All adverse events with an onset date on or after Day 1 of study medication until 28 days after the last dose of study medication will be summarized (with frequency and percentage) by System Organ Class (SOC), preferred term (PT) within SOC, and

Nutropin AQ (Somatropin [rDNA origin])—Genentech, Inc. 11/Statistical Analysis Plan ML29543 severity grade. In the adverse event summaries, a patient having the same event more than once will be counted only once for that event type. For adverse events of varying severity, the highest (worst) grade will be used in the summaries. Missing severity or relationship to study drug will not be imputed.

Summaries of the following adverse events will be provided:

- AEs by SOC and PT
- SAEs by SOC and PT
- AEs by SOC, PT and severity
- AEs by SOC, PT and relationship to study medication

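### The 28-day safety call is scheduled only after the Month 12 visit, so a child who leaves the study early may have no scheduled contact for part of the adverse event window

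*Protocol*

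**What the plan says.** **The window.** Protocol 5.3.1 requires all serious and non-serious events, once drug has started, "regardless of relationship to study drug, will be reported until 28 days after the last dose of study drug as provided in this study". Section 5.4.2 and Appendix 1 footnote q set the same limit. SAP 4.6.2 tabulates the same period: "All adverse events with an onset date on or after Day 1 of study medication until 28 days after the last dose of study medication".

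**How events are found.** Section 5.3.1 has investigators ask about adverse events whenever they are in contact with the patient. Section 5.3.2 describes open questioning at evaluation timepoints.

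**The late contact.** The Safety Follow-Up column of Appendix 1 is defined by footnote c: "The patient will be contacted by phone 28 ± 3 days after the Month 12 visit to collect adverse events". Section 3.1, the synopsis and the SAP's copies (its Appendices 1 and 2) agree. None of them mentions a call for anyone else.

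**The exit visit.** The timing is worded in two ways:
- Footnote d reads: "Patients who discontinue from the study early will be asked to return to the clinic within 28 days after the last dose of study drug". Section 4.5.5 says that "an early discontinuation visit should be scheduled within 28 days after the last dose of Nutropin AQ v1.1", and footnote l repeats this.
- The synopsis: "within 28 (± 3 days) days after the last dose of study drug for an early discontinuation visit". Section 3.1 and the synopsis copy in SAP Appendix 1 also carry the ± 3 days.

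**Related provisions.** Under Section 4.6.2 a child who stops drug may stay in the study and keep to the visit schedule, adverse event reporting included. Under 4.6.1 nobody is followed after consent is withdrawn. Under 5.5.1 each known event is followed until it resolves, is judged stable, the child is lost, or consent is withdrawn.

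**The concern.** The reporting window is counted from the last dose and applies to every treated child. The contact that closes it is counted from the Month 12 visit, which a child who leaves the study early never has. For that child the last scheduled contact is the exit visit, which has an upper limit but no earliest day. If the visit comes soon after the last dose, the remaining days of the window contain no occasion on which anyone is due to ask about new events.

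What is at stake is the completeness of the safety tables for early leavers. An event that first appears after the exit visit, but inside the 28 days, belongs in the SAP 4.6.2 summaries. It will be there only if the family volunteers it or the site happens to be in touch. The primary antibody endpoint does not depend on this call.

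**Working it through.** The plan gives no figure for this gap, so there is nothing of its own to reproduce. The check compares the schedule with the window and then does simple arithmetic.

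**Inputs**
- Window: 28 days from the last dose (Protocol 5.3.1; SAP 4.6.2).
- Safety call: day 28 ± 3 from the Month 12 visit (footnote c).
- Exit visit: latest day 28 in 4.5.5 and footnotes d and l; the same with ± 3 days in 3.1 and the synopsis.
- Lower limit on the exit visit: none as a day. The only constraint is that its blood sample be taken at least 12 hours after the last dose (4.3.2, footnote o), so a visit on day 1 complies.
- Enrollment 80 and projected dropout 10–15% (Protocol 6.1).
- Actual day of the exit visit: not given in the documents.

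**Step 1. Days without a scheduled contact, for one child**

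Gap = max(0, 28 − exit-visit day).

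| Exit visit, days after last dose | Gap (days) | Share of window |
|---|---|---|
| 1 | 27 | 96% |
| 3 | 25 | 89% |
| 7 | 21 | 75% |
| 14 | 14 | 50% |
| 21 | 7 | 25% |
| 25 | 3 | 11% |
| 28 or later | 0 | 0% |

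**Step 2. The two readings of the visit timing**
- *Any day up to 28* (4.5.5, footnotes d and l as they stand): the gap runs from 0 to 27 days.
- *A target of day 28 with a tolerance of 3* (one way to take 3.1 and the synopsis): the visit falls on days 25 to 31, and the gap is at most 28 − 25 = 3 days.

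**Step 3. How many children**

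80 × 0.10 = 8 and 80 × 0.15 = 12. This is all projected dropout, so it is a ceiling at those rates.

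**Step 4. Patient-days, under assumed visit days**

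The total window for early leavers is 8 × 28 = 224 to 12 × 28 = 336 patient-days. Of these, the days without a scheduled contact would be:
- all visits on day 3: 8 × 25 = 200 to 12 × 25 = 300;
- visits spread evenly over days 1–28 (mean gap 13.5 days): 8 × 13.5 = 108 to 12 × 13.5 = 162;
- all visits on day 25, the worst case of the second reading: 8 × 3 = 24 to 12 × 3 = 36;
- all visits on day 28: 0.

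**The case against.** The strongest reply is the ± 3 days. A tolerance of that kind fits a visit aimed at day 28 better than a visit on any day, and the exit visit already collects adverse events. On that reading the gap is trivial. This stands as a possible reading, but not as a settled one: Section 3.1 and the synopsis still say *within*, and 4.5.5 and footnotes d and l have no tolerance at all.

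Other parts of the reply stand and limit the point:
- **The reporting duty.** It runs to day 28 for every treated child. A reader might infer that the window is simply not covered for early leavers. What is missing is a scheduled contact, not the obligation.
- **Children who stop for an event named in 5.1.1.** A reader might infer that collection is thinnest for them. The documents do not support this. Section 5.5.1 follows known events, 5.3.5.4 records worsening, and follow-up contacts are themselves occasions to ask about new events. These children may also stay on the visit schedule under 4.6.2.
- **The denominator.** A reader might infer that the SAP credits early leavers with 28 days of observation. It does not. SAP 4.6.2 plans counts and percentages of patients, SAP 4.6.1 ends exposure at the last treatment date, and SAP 4.2 ends participation at the last assessment.
- **Completers.** A call at day 25 can miss about 3 days at most. That is an ordinary visit tolerance and a minor matter.

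**Conclusion.** The point holds as a gap in eliciting new events among children who leave the study early. The documents place a contact at the end of the 28-day window for completers and none for early leavers, and they word the exit visit in two ways that lead to very different gaps.

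The gap for one child is up to 27 days if the visit may fall on any day, and at most 3 days if it is meant as day 28 ± 3. At most 8–12 of 80 children are concerned at the projected dropout. The number falls once those who withdraw consent, those seen near day 28, and those who stop drug but stay on schedule are set aside. The documents do not allow those groups to be sized. The 27 days should not be read as an expected value, because no document gives a typical exit-visit day.

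The consequence is possible under-counting of late new events in a small group. It is worth correcting because the correction is cheap, not because it threatens the study's main conclusion.

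**What to change.** 1. Reconcile the exit-visit timing across Protocol 3.1, 4.5.5, Appendix 1 footnotes d and l, the synopsis, and the SAP's copies in its Appendices 1 and 2, so that one statement makes clear whether an earliest day applies.
2. Extend the existing safety call in footnote c, 3.1 and both synopses to treated patients who leave the study early and have not withdrawn consent. For them, count it from the last dose and make it on or after day 28. Waive it where the exit visit already falls on or after day 28.
3. Show this in the schedule, so that the Safety Follow-Up column visibly applies to early leavers.

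The cost is a text amendment and at most about 8–12 phone calls. The call and its place in the schedule already exist. The change concerns data collection only; the analysis in SAP 4.6.2 stays as written.

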Appendix 1 (cont.) Schedule of Assessments

- The first dose (Day 1, baseline visit) should occur after the patient receives dosing administration instruction in the clinic and after the initial blood sample is drawn. Blood samples scheduled after baseline (Months 1, 3, 6, 9, and Month 12 or early discontinuation) should be taken at least 12 hours after the last dose of Nutropin v1.1 and prior to the next dose.
- ^{*p*} Assess compliance with daily dosing at each visit after baseline. Reinstruct patients and caregivers, as needed.
- ^q After initiation of study drug, all serious adverse events and non-serious adverse events, regardless of relationship to study drug, will be reported until 28 days after the last dose of study drug as provided in this study. After this period, the investigator should report any serious adverse events that are believed to be related to study drug. The Sponsor should be notified if the investigator becomes aware of any serious adverse event that occurs after the end of the adverse event reporting period (defined as 28 days after the last dose of study drug), if the event is believed to be related to prior study drug treatment. The investigator should follow each adverse event until the event has resolved to baseline grade or better, the event is assessed as stable by the investigator, the patient is lost to follow-up, or the patient withdraws consent. Every effort should be made to follow all serious adverse events considered to be related to study drug or trial-related procedures until a final outcome can be reported.

Nutropin AQ (Somatropin [rDNA origin])—Genentech, Inc. 60/Protocol ML29543, Version 2
